2.2 Study Population and Sites

The study will examine the medical records of patients who underwent cardiac surgery in Massachusetts between 1/1/2012 to 12/31/2016. It is estimated that ~50,000 patients are eligible for inclusion in this study. The evaluable sample size is derived from a sample of convenience from the following Institutions.

Baystate Medical Center, Springfield, MA
Beth Israel Deaconess Medical Center, Boston, MA
Brigham and Women's Hospital, Boston, MA
Cape Cod Hospital, Hyannis, MA
SouthCoast Health, Fall River, MA
Massachusetts General Hospital, Boston, MA
Mount Auburn Hospital, Cambridge, MA
UMass Memorial Medical Center-University, Worcester, MA

Tufts Medical Center, Boston, MA

2.3 Primary Aims

The Primary Aims of this study are to determine:

1. The risk factors, which includes the main risk factor preoperative atrial fibrillation, for postoperative atrial fibrillation occurring after discharge from hospital in patients who underwent cardiac surgery during admission.
2. The risk factors, which includes the main risk factor preoperative atrial fibrillation, for stroke or other focal neurologic event occurring after discharge from hospital in patients who underwent cardiac surgery during admission.

2.4 Secondary Aims

The Secondary Aims of this study are to determine:

1. The frequency of, and treatments for, atrial fibrillation occurring after discharge from hospital in patients who underwent cardiac surgery during admission.
2. The frequency of stroke or other focal neurologic event occurring after discharge from hospital in patients who underwent cardiac surgery during admission
3. The incidence of all-cause and stroke-related mortality after cardiac surgery.

3 STUDY ENDPOINTS AND COVARIATES

3.1 Definitions of Study Endpoints

1. Postoperative atrial fibrillation occurring after discharge from hospital
2. Stroke or other focal neurologic event occurring after discharge from hospital
3. All-cause mortality
4. Stroke-related mortality

3.2 Definitions of Covariates

Data derived from individual sites will use definitions from the Society of Thoracic Surgeons Adult Cardiac Surgery Database versions 2.7.3 and 2.8.2 (43,44).

3.3 Modifications or derivations of standard variables

Hospital admissions will be defined using continuous in-patient stays (CIS) which combine data from each event within hospital, which includes within hospital transfers. Diagnostic subgroups will be defined using the code recorded for the main diagnosis for the first event within a CIS. The ninth

International Classification of Disease codes (ICD-9) codes will be used to define the specific conditions of interest.

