2 STUDY SUMMARY AND AIMS

The purpose of this study is to determine the incidence, risk factors and adverse events consequent upon atrial fibrillation after cardiac surgery, as well as the association between prior atrial fibrillation and postoperative atrial fibrillation. The study uses information from local Cardiac Surgical Programs to describe the preoperative medical state and immediate post-operative state. Additionally, information from the post-discharge period will be provided by CHIA, by matching the two sources of information using HIPAA-waived data such as medical record number, date of birth, gender and last name. Once matched, the data are stripped of identifiers.

2.1 Study Design:

We will employ a retrospective cohort design, examining patients who underwent cardiac surgery at Cardiac Surgical Programs in Massachusetts between 1/1/2012 and 12/31/2016, with a follow-up period that extends to 12/31/2017. The study examines the risk factors and incidence of post-operative atrial fibrillation, stroke and other focal neurological events after discharge from hospital.

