7.1.1 Primary Aims

The standard Cox proportional hazards model will be used to model time to first atrial fibrillation occurrence and time to first stroke or other focal neurologic event, after discharge from hospital,

respectively. The potential risk factors included will be selected based on their univariate association with first event status, as well as clinical significance. Hazard ratios with 95% confidence intervals will be reported with a two-sided p-value for statistical significance. The proportional hazard assumption will be evaluated using graphical tool, and by including time dependent covariate terms.

Since there might be repeated occurrences of atrial fibrillation and stroke or other focal neurologic event for each patient, we will use the Andersen-Gill (AG) model and the Prentice, Williams and Peterson (PWP) models to analyze recurrent events data. The AG model is suitable when the interest is in the overall effect on the intensity of the occurrence of a recurrent event. The PWP models allow us to evaluate the effects of risk factors for the kth event after discharge from hospital, as well as the effects of risk factors for the kth event since the time from the previous event (47). Hazard ratios with 95% confidence intervals will be reported with a two-sided p-value for statistical significance. For time-to-event data analyses, death will be considered a censoring event.

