10 APPENDIX: CHIA-SOURCED VARIABLE DEFINITIONS AND ABSTRACTION

We will create a subset of cardiac surgery patients using all three CHIA databases to maximize the chance of finding a matching cardiac surgery record in RPDR. UHINs for the cardiac surgery cases are identified in the inpatient database where at least one of 15 procedure codes or principal procedure contains an ICD9-CM code for cardiac surgery (3610-3619). The following lists the minimum set of fields needed to complete the merge.

- a. MDPHHospNum: MDPH hospital number determined from all hospital IDs in the case mix data
- b. AdmitDt: Admission date to hospital
- c. ProcDates: Possible dates for cardiac surgical procedure (15 in inpatient, 3 in OOR data)
- d. ProcedureCodes: ICD-9-CM and CPT (OOR only) codes for cardiac surgery records (only 3 ICD-9-CM in OOR data)
- e. PrincipalProcDate: Date for principal procedure (OOR only)
- f. PrincipalProcedure: ICD9-CM code for PCI and CABG records
- g. Diagnosis Codes: Diagnosis and DRG codes for conditions
- h. DischDate: Discharge date from hospital
- i. RecordType20ID: CHIA Record Id Control Number
- j. UHIN Unique patient identifier from CHIA
- k. DOB: Patient date of birth submitted by hospital
- l. MedicalRecordNum: Hospital patient medical record number
- m. Gender: Patient gender

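### Section 3.3 and Appendix 10 use ICD-9 codes only, with CHIA follow-up to the end of 2017; if the records change code system before then, late operations go unmatched and later AF and stroke go undetected.

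*Combined protocol and SAP*

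**What the plan says.** - Section 3.3 gives the only statement of a code system for conditions. The ninth "International Classification of Disease codes (ICD-9) codes will be used to define the specific conditions of interest". No list of AF, stroke, focal-event or fracture codes is given in any system.
- Section 2.1 places surgery "between 1/1/2012 and 12/31/2016, with a follow-up period that extends to 12/31/2017".
- Section 2 states that "information from the post-discharge period will be provided by CHIA". In the Table 1 shell, every timed post-discharge AF and stroke band is sourced to CHIA.
- Appendix 10 identifies the inpatient surgery cases as those where "at least one of 15 procedure codes or principal procedure contains an ICD9-CM code for cardiac surgery (3610-3619").
- Section 7.1.1 sets the primary model: "The standard Cox proportional hazards model will be used to model time to first atrial fibrillation occurrence and time to first stroke". Focal neurologic events of other kinds count together with stroke. The only censoring event named in that section is death: "For time-to-event data analyses, death will be considered a censoring event".
- Section 7.1.2 models frequencies by Poisson regression and takes follow-up length as the offset.

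ICD-10 is not mentioned anywhere: there is no list, crosswalk or date rule.

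**The concern.** A diagnosis search in one code system works only while the records use that system. If CHIA records move to another system before 12/31/2017, the plan as written has two separate effects.

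1. **Operations after the change.** The inpatient search would not find the surgical admission. These patients would mostly leave at the unmatched step of Figure 1.
2. **Operations before the change.** These patients are matched and stay at risk, but AF, stroke and negative-control fractures after the change cannot be detected. Neither the risk set nor the Poisson offset is shortened, so the blind period counts as event-free time.

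Secondary Aims 1 and 2 and Figures 2 and 3 depend directly on complete capture. The primary hazard ratios depend on the number of events. The negative-control check in 3.4 would also lose events. A fuller ICD-9 procedure list would leave the same gap.

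**Working it through.** **Inputs from the plan.** Surgery 1/1/2012 to 12/31/2016 and follow-up to 12/31/2017 (2.1); 50,000 patients, 4,000 with prior AF and so 46,000 without, 25% incidence without prior AF, a 2-point difference, two-sided 0.05 (section 4).

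**Assumptions, not in the documents.** ICD-9 stops in the records on 1 October 2015, varied from 1/1/2015 to 1/1/2017; uniform accrual; no deaths; either a constant hazard or a front-loaded one (Weibull shape 0.4).

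**Step 1: the plan's own figure.** Detectable h = (1.960 + 0.842) × √(1/4,000 + 1/46,000) = 0.0462, against the stated 0.046. For 25% vs 27%, power = Φ[(0.02 − 1.96 × SE0)/SE1], with pooled SE0 = 0.00715 and unpooled SE1 = 0.00730, so Φ(0.819) = 79.4%, against the stated 80%. The sample-size text reproduces.

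**Step 2: person-time.** Count years from 1/1/2012, so accrual is 0 to 5, follow-up ends at 6, and the change is at c = 3.75.
- Operated on after the change: (5 − 3.75)/5 = 25%, or 12,500 of 50,000.
- Total person-time, per unit accrual rate: 6 × 5 − 5²/2 = 17.5.
- Patients operated on before the change: total 6 × 3.75 − 3.75²/2 = 15.47, of which blind 3.75 × 2.25 = 8.44. Share 8.44/15.47 = 54.5%.
- Patients operated on after it: 17.5 − 15.47 = 2.03, all blind.
- If everyone is kept: (8.44 + 2.03)/17.5 = 59.8%.

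**Step 3: first AF events lost.** Calibrate each hazard so that full follow-up of the whole cohort gives 25% without prior AF and 27% with it. The constant hazards are 0.0843 and 0.0925 per year (ratio 1.097). The front-loaded cumulative hazards are 0.1793 t^0.4 and 0.1962 t^0.4 (ratio 1.094). For 1 October 2015, without prior AF:
- Before-change patients, constant: 14.27% captured of a true 29.08%, loss 1 − 14.27/29.08 = 51%.
- Before-change patients, front-loaded: 19.36% of 26.85%, loss 28%.
- All kept, constant: 10.70% of 25%, loss 57%. Front-loaded: 14.52% of 25%, loss 42%.

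**Step 4: power on captured incidence, all patients kept.** Constant: 10.70% vs 11.62% gives 44.0%. Front-loaded: 14.52% vs 15.72% gives 54.1%. If late patients drop out instead, 34,500 and 3,000 remain and the incidences are those values divided by 0.75 (14.27% vs 15.49%; 19.36% vs 20.96%). Power is then 45.4% and 56.5%, much the same.

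**Range over the assumed date** (loss and power: front-loaded, then constant):

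| Change | Operated on after | Blind time, before-change patients | Blind time, all kept | First AF lost, before-change patients | First AF lost, all kept | Power, all kept |
|---|---|---|---|---|---|---|
| 1/1/2015 | 40% | 66.7% | 74.3% | 36%, 63% | 57%, 72% | 42.2%, 31.5% |
| 10/1/2015 | 25% | 54.5% | 59.8% | 28%, 51% | 42%, 57% | 54.1%, 44.0% |
| 1/1/2016 | 20% | 50.0% | 54.3% | 25%, 47% | 37%, 52% | 58.0%, 48.4% |
| 1/1/2017 | 0% | 28.6% | 28.6% | 14%, 26% | 14%, 26% | 72.7%, 66.0% |

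**Step 5: a check against the table shell.** Table 1 has AF and stroke rows for 4 to 5 years. With surgery from 1/1/2012, no patient reaches year 4 before 1/1/2016. For any change on or before that date, those rows would be zero whatever happened to the patients.

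**The case against.** - **The date is external.** Nothing in the documents says when, or whether, CHIA records stop carrying ICD-9. A reader might infer that late AF and stroke will certainly be recorded as no event. The documents do not support that: the consequence is conditional, and its size moves with the date.
- **Section 3.3 does not name the endpoints.** It speaks of conditions of interest, after a sentence on diagnostic subgroups. Applying it to AF, stroke and fractures is an inference, though no other text supplies codes for them. Appendix 10 also lists a diagnosis and DRG field with no ICD version, and CPT for the OOR data, so the appendix is not ICD-9 throughout. The inpatient search for the operation is.
- **Late patients are not simply event-free.** The cohort comes from local STS databases and is linked to CHIA. Those operated on after the change would mostly be lost at matching, so 54.5% is the better figure for blind time and 60% applies only if they are kept.
- **Half to 60% is the upper end.** A reader might take the 60% blind time as the share of events lost. That holds for a total event rate that is constant over time. Capture of first events is better if AF clusters early.
- **The primary aims are hazard ratios.** If missed events are unrelated to prior AF and hazards are proportional, the prior-AF ratio is not strongly biased. A reader might infer that the primary estimate is distorted; the documents do not show that.
- **Some of the pattern is there by design.** A December 2016 operation has about one year of follow-up, so 4- to 5-year events come only from early operations even with perfect coding.

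All six points stand and limit the claim. None supplies a code list or a censoring rule. Analysts might well add ICD-10 in practice, but the SAP is meant to fix the analysis, and its timeline places the work in 2018, after follow-up has ended.

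**Conclusion.** The point holds in conditional form. The plan states an ICD-9-only rule, runs follow-up to 12/31/2017, and has no provision for a coding change. If the records leave ICD-9 on 1 October 2015, about 25% of patients would mostly go unmatched, and 54.5% of the remaining patients' person-time would be blind. Those patients would lose roughly 28% to 51% of first AF events (42% to 57% if all patients are kept).

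The clear bias is downward, in AF and stroke frequencies, in the Poisson rates and in Figures 2 and 3. For the prior-AF hazard ratio the main cost is events and power: about 79% falls to 44%-54%, under the two conditions given above. Mortality, sourced in Table 1 to the surgical programs, is not exposed to this gap. The figures rest on the assumed date, uniform accrual, no deaths and the two hazard shapes. Even with the latest date examined, 29% of person-time is blind. This should be corrected before analysis.

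**What to change.** In section 3.3 and Appendix 10, define AF, stroke or other focal neurologic event, the negative-control fractures and each qualifying operation with paired ICD-9-CM and ICD-10-CM/PCS lists, applied by discharge date. State the date on which the CHIA records change system. Plot AF and stroke rates by calendar quarter across that date.

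If only ICD-9 can be used, end accrual at the last ICD-9 date, censor follow-up there, and shorten the Poisson offset to match.

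The cost is SAP wording and code lists; no new data source or patients are needed. The small downside is a possible step in coded rates at the change, to be examined in a sensitivity analysis with coding era as a stratum.

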3.4 Unrelated outcomes

Un-related events such as upper or lower limb fracture and xxx will be used as negative controls.

Unrelated adverse events (such as upper or lower limb fracture), which are known not to be caused by prior AF will be used as the composite negative control outcome to examine whether there is unmeasured confounders of the prior AF-postoperative AF association. An observed association between prior-AF and the negative control outcome will reflect the existence of unmeasured confounders. In such cases, these unmeasured confounders will also affect the true prior AF-postoperative AF association (45). When such unmeasured confounding effect is detected, we will provide an adjusted estimate for the hazard ratio of first postoperative AF using an indirect approach (46)

4 ESTIMATION OF ACCESSIBLE EFFECT SIZE

This will be a retrospective cohort study. Patients will be included in the study based on the inclusion and exclusion criteria. All statistical tests will be two-sided and the statistical significance level will be set at 0.05 unless otherwise stated. Assuming 50,000 patients will be included in the analysis, among which 4000 (8%) have prior AF, we will have 80% power to detect a Cohen's effect size of 0.046 at the 0.05 significance level. If 25% of the patients who do not have prior AF have postoperative AF, a Cohen's effect size of 0.046 is corresponding to a 2% difference in the incidence of postoperative AF.

5 DATA SOURCES

6 STUDY POPULATIONS

6.1 Inclusion Criteria

Inclusion criteria for this study are patients who undergo surgical procedures that include coronary artery bypass graft surgery, aortic valve surgery or mitral valve surgery and other valvular surgical procedures.

6.2 Exclusion Criteria

Exclusion criteria for this study are:

Preoperative status

Prior AF ablation or pulmonary vein isolation procedure of any type

Prior LA occlusion or ablation procedure of any type

Surgical procedure

MAZE or other procedure for the treatment or prevention of AF

Ventricular assist device
Heart transplantation
Bacterial endocarditis
Cardiac trauma
Cardiac tumor
Ventricular septal defect repair
Left ventricular aneurysm repair
Pulmonary thromboendarterectomy
Surgical ventricular restoration

6.3 Subgroups

Subgroups may be used in secondary analyses.

6.4 Description of participants

The study participants will be presented as per the CONSORT recommendations (Figure 1). The baseline characteristics will be presented (Table 1). Including:

Demographic characteristics (e.g., age, sex, socioeconomic status)
Baseline exposure characteristics (e.g., smoke exposure)
Baseline disease characteristics

Table 2 (Appendix) will describe the baseline characteristics of the study group comparing patients with post-discharge AF, compared to those without.

Baseline values of primary and/or secondary outcome variables

7 STATISTICAL ANALYSES

7.1 General

Baseline and demographic characteristics will be summarized using descriptive statistics (means, standard deviations or median, interquartile ranges for continuous variables such as age and percentages for categorical variables such as race and ethnicity. When deemed appropriate, they will be compared using Chi-square test, Fisher's exact test, two-sample t test, and Wilcoxon rank-sum test between groups. For each binary outcome we will report odds ratios with 95% confidence intervals and give a two-sided p-value for statistical significance. For analysis of the pre-specified subgroups (primary outcome only) we will report relative risks with 99% confidence intervals with two-sided p-value.

7.1.1 Primary Aims

The standard Cox proportional hazards model will be used to model time to first atrial fibrillation occurrence and time to first stroke or other focal neurologic event, after discharge from hospital,

respectively. The potential risk factors included will be selected based on their univariate association with first event status, as well as clinical significance. Hazard ratios with 95% confidence intervals will be reported with a two-sided p-value for statistical significance. The proportional hazard assumption will be evaluated using graphical tool, and by including time dependent covariate terms.

Since there might be repeated occurrences of atrial fibrillation and stroke or other focal neurologic event for each patient, we will use the Andersen-Gill (AG) model and the Prentice, Williams and Peterson (PWP) models to analyze recurrent events data. The AG model is suitable when the interest is in the overall effect on the intensity of the occurrence of a recurrent event. The PWP models allow us to evaluate the effects of risk factors for the kth event after discharge from hospital, as well as the effects of risk factors for the kth event since the time from the previous event (47). Hazard ratios with 95% confidence intervals will be reported with a two-sided p-value for statistical significance. For time-to-event data analyses, death will be considered a censoring event.

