1.2 Background Literature

Atrial fibrillation (AF) is the most common cardiac arrhythmia and frequently presents in association with mitral, other valvular and coronary artery disease, notably in the presence of poorer left ventricular function (1,2). Preoperative AF is reported commonly in patients undergoing cardiac surgery, with an incidence of 10-20% (2-8). Even if treated, preoperative AF is associated with a higher incidence of in-hospital postoperative AF, stroke, other cardiac morbidity and mortality (2,6,9-11).

Conventional management of postoperative AF assumes that it results from self-limited causes, such as postoperative pericarditis, surgical stress, and sympathetic stimulation in patients underlying heart disease that can be treated with short-term antiarrhythmics, heart rate reduction, anti-coagulants and anti-platelet agents. However, it is well-known that AF in the immediate postoperative period is associated with increased risk of post-discharge AF and stroke. Observed incidences range widely (3-25%) depending principally on the duration of follow-up and the mode of monitoring (12-14). These studies did not use continuous ECG monitoring to detect AF recurrence, and therefore may have underestimated the incidence of AF by missing asymptomatic AF. Using continuous ECG monitoring the incidence of at least one electrocardiographic episode of AF lasting longer than six minutes is much higher; 60% over the entire follow-up period and 39% occurring more than 3-months after surgery (15).

Thromboembolic stroke is a major preventable cause of morbidity and mortality in patients with post-operative AF (16-18). Studies have demonstrated a risk-unadjusted two to ten-fold increase in embolic events and a threefold increased risk of cardiac death in patients with postoperative AF (12,19,20).

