7.1.2 Secondary Aims

Means and standard deviations will be estimated for count outcomes. We will report the two-sided p-value for statistical significance of the difference in means of count outcomes.

The frequencies of atrial fibrillation and stroke or other focal neurologic event will be modeled with Poisson regression with the length of follow-up time as the offset. Potential risk factors included in this model will be selected based on univariate test results, as well as clinical significance. Logistic regression will be used to model the incidence of all-cause and stroke-related mortality after cardiac surgery, respectively.

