7.4 Statistical Analytical Issues

7.4.1 Adjustments for covariates

There will be covariate adjustment in the primary analysis.

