63	Prior other valve surgery	CSP	PrValveProc1, PrValveProc2, PrevProcAVReplace , PrevProcAVRepair , PrevProcTVReplace , PrevProcTVRepair , PrevProcPV , PrevProcAVBall , PrevProcMVBall , PrevProcTCVRep , PrevProcPercVRepair
64	Other cardiac surgery	CSP	PrOthCar, PrOthCongen, POC, POCInt1, POCInt2, POCInt3
65	Prior ICD placement	CSP	PrOCAICD
66	Prior pacemaker placement	CSP	PrOCPace
67	Prior arrhythmia surgery	CSP	POArr
69			
70	Preoperative laboratory testing		
77	White cell count (10^6 /dL)	CSP	WBC
78	Creatinine (mg/dL)	CSP	CreatLst
79			
80	Preoperative Cardiac Imaging		
81	Number of diseased coronary vessels	CSP	NumDisV
82	0		
83	1		
82	2		
83	≥ 3		
84	LV Ejection fraction	CSP	HDEF
85	<30%		
86	30-54%		
87	$\geq 55\%$		
88	Aortic stenosis	CSP	VDStenA
89	Aortic insufficiency	CSP	VDInsufA
90	Mitral stenosis	CSP	VDStenM
91	Mitral insufficiency	CSP	VDInsufM
92	Tricuspid valve disease	CSP	VDStenT, VDStenP
93	Pulmonary valve disease	CSP	VDStenP, VDInsufP

94

95 **Surgery**

[figure not shown]
96	Year of operation	CSP	SurgDt
97		2012	
98		2013	
99		2014	
100		2015	
101		2016	
101	CABG surgery	CSP	OpCAB
102	Number of conduits placed	CSP	DistArt + DistVein
103		1	
104		2	
105		>=3	
106	AVR surgery	CSP	VSAVPr, VSAV
107	MVR surgery	CSP	OpMitral, VSMVPr, VSMV
108	Other valve surgery	CSP	OpPulm, VSPV, OpTricus, VSTV
109	Ascending aortic surgery	CSP	AortProcTotArch, ONCArch, AortProcHemi, AortProc , OpAortic, OCAoProcType, AortProcRoot, ONCAoRt, AortProcAsc, ONCAsc, ONCAsc
110	Other non-CABG, non valvular surgery	CSP	OpOCard
111	Atrial septal surgery	CSP	OCarASD, OCarASDPFO
114	Ventricular outflow tract surgery	CSP	OCarSubaStenRes , ResectSubA
115	Congenital heart surgery		OCarCong , OCarCongProc1 , OCarCongProc2 , OCarCongProc3
116	Carotid endarterectomy	CSP	
117	Reoperation	CSP	Incidenc
118	Surgical urgency	CSP	Status
119		Elective	
120		Urgent	
121		Emergent	
122	Postoperative duration (days)	CSP	DischDt - SurgDt
123			
124	Post-operative complications		

125	Stroke	CSP and CHIA	CNSTrokP
126	TIA	CSP and CHIA	CNSTrokTTIA
127	Atrial fibrillation	CSP and CHIA	COAtFib
128	Reoperation for bleeding	CSP and CHIA	COpReBld
129	Pacemaker inserted	CSP and CHIA	CRythmDis
130	In-hospital atrial fibrillation	CSP	COAtFib
131	In-hospital atrial flutter	CSP	
132			
133	Discharge medications and devices		
134	Aspirin	CSP and CHIA	DCASA
135	Warfarin	CSP and CHIA	DCCoum
136	Anti-platelet agent	CHIA	-
137	Beta blocker	CSP and CHIA	DCBeta
138	Amiodarone	CSP and CHIA	DCAmiodarone

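### The covariate rule for the primary Cox models does not keep post-exposure variables out, so in-hospital AF would very likely enter and remove part of the prior-AF hazard ratio

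*Combined protocol and SAP*

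**What the plan says.** Section 2.3 sets the first primary aim as "The risk factors, which includes the main risk factor preoperative atrial fibrillation, for postoperative atrial fibrillation occurring after discharge from hospital". The second primary aim has the same form, with stroke or another focal neurologic event as the outcome. Both outcomes are analysed as time to first event after discharge by Cox regression (section 7.1.1), with this rule for covariates: "The potential risk factors included will be selected based on their univariate association with first event status, as well as clinical significance". Section 7.1.2 repeats the rule for the Poisson models: "Potential risk factors included in this model will be selected based on univariate test results, as well as clinical significance".

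On adjustment, section 7.4.1 says only "There will be covariate adjustment in the primary analysis". Two other rules can remove a variable: a variance inflation factor above 2.5 (section 7.4.4) and more than 33% missing (section 7.3). Neither concerns when the variable was measured.

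The Table 1 shell in Appendix 12 lists "In-hospital atrial fibrillation" among the post-operative complications, and has a block headed "Discharge medications and devices". Section 6.4 describes Table 1 as showing baseline characteristics.

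Section 3.4 uses an unrelated outcome "to examine whether there is unmeasured confounders of the prior AF-postoperative AF association". Section 7.6 extends this to stroke and all-cause mortality and adds E-values.

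**The concern.** Prior AF is the named main risk factor, and it is fixed before surgery. In-hospital AF, complications and discharge drugs all come later. A screen that looks only at association with the outcome cannot tell a confounder of prior AF from a consequence of it. When a consequence that itself raises the risk of the outcome is adjusted for, the prior-AF coefficient stops being a total effect and becomes a direct effect that excludes that route.

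The plan never says which of the two it wants. An analyst could follow the SAP to the letter and report either, and a reader could not tell which had been pre-specified. The sensitivity analyses would not reveal the difference. A negative-control outcome and an E-value ask whether an unmeasured common cause could produce the association. They do not ask whether a measured intermediate has been conditioned on.

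**Working it through.** **1. The plan's own figure.** Section 4 assumes 50,000 patients, 4,000 of them with prior AF, two-sided 0.05 and 80% power, and states a detectable Cohen's effect size of 0.046, or 2 percentage points from 25%.

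- h = (1.960 + 0.842) × √(1/4,000 + 1/46,000) = 0.0462.
- Converting back: sin²[(2·arcsin√0.25 + 0.046)/2] = 0.270, a difference of 2.0 points.

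The figure reproduces. The present point does not change it.

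**2. Are both legs of the path in the documents?** Section 1.2 reports a higher incidence of in-hospital postoperative AF in patients with preoperative AF. It then says that "AF in the immediate postoperative period is associated with increased risk of post-discharge AF and stroke". In-hospital AF therefore sits between the exposure and both primary outcomes on the plan's own account.

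**3. Would it pass the screen?** Section 4's inputs imply 0.25 × 46,000 + 0.27 × 4,000 = 11,500 + 1,080 = 12,580 first AF events. Assume a covariate with 30% prevalence and a 0.05 cut-off; the plan gives neither. Schoenfeld's formula gives power = Φ(|ln HR| × √(12,580 × 0.3 × 0.7) − 1.96), where the root is 51.4.

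- HR 1.05: Φ(2.51 − 1.96) = 71%.
- HR 1.10: Φ(4.90 − 1.96) = 99.8%.
- HR 1.20: Φ(9.37 − 1.96), about 100%.

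At this size the screen rejects almost nothing that is related to later AF. Section 1.2 also gives a clinical reason to include in-hospital AF. The documents give no event count for stroke, so the same calculation cannot be made there.

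**4. What does adjusting for it do?** All inputs here are assumptions: direct prior-AF HR 1.5, and in-hospital AF in 30% without prior AF and in p₁ with it, carrying HR m. As an approximation, the total HR = 1.5 × [1 + p₁(m − 1)] / [1 + 0.3(m − 1)], and the share of the log HR lost on adjustment is 1 − ln 1.5 / ln(total HR). The last two columns are from Cox models fitted to one simulated data set per scenario (50,000 patients, 8% exposed, follow-up spread over 1 to 6 years), so they carry some chance variation.

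| p₁ v 30%, m | Formula: total HR | Share lost | Simulated HR, unadjusted to adjusted | Share lost |
|---|---|---|---|---|
| 40%, 2 | 1.5 × 1.4/1.3 = 1.62 | 15% | 1.68 to 1.58 | 12% |
| 50%, 2 | 1.5 × 1.5/1.3 = 1.73 | 26% | 1.68 to 1.47 | 26% |
| 60%, 3 | 1.5 × 2.2/1.6 = 2.06 | 44% | 2.03 to 1.54 | 39% |

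Outside that range, also simulated:

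- Direct HR 1.1 (60% v 30%, m = 3): 1.479 falls to 1.075, so 81% of the log HR goes.
- Direct HR 1.0 (60% v 30%, m = 2): 1.18 falls to 0.97, so all of it goes.
- In-hospital AF unrelated to prior AF (30% v 30%, m = 3): 1.43 against 1.46, so nothing is lost. This case conflicts with section 1.2.

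**The case against.** The strongest reply is that the plan never says these variables enter. Clinical significance is a second, undefined criterion that could keep them out, and the collinearity and missingness rules could drop some. Appearing in Table 1 proves little, since that shell also lists the outcomes. This stands. A reader might infer that the rule necessarily puts in-hospital AF and discharge drugs into the model. The documents support only that nothing excludes them and that in-hospital AF would very likely qualify.

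A reader might also infer that adjusting for discharge drugs shrinks the prior-AF hazard ratio. That does not follow. If a drug is given more often to patients with prior AF and lowers risk, adjusting for it raises the hazard ratio.

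Nor do the documents show that the screen drops important confounders or makes intervals materially too narrow. With about 12,580 implied AF events it removes little, and clinical significance allows a masked confounder to be kept. Section 7.1.1 does not name the univariate test either, so it is not established that the screen ignores follow-up time.

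Finally, the aims speak of risk factors in the plural, and in-hospital AF is a legitimate predictor at discharge. This is true for a prognostic model. It does not settle what the prior-AF coefficient means when prior AF is singled out as the main risk factor and its association alone is probed for unmeasured confounding.

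**Conclusion.** The concern holds in a limited form. The rule leaves the adjustment set open to post-exposure variables, and section 1.2 makes in-hospital AF a very likely entrant. Its inclusion would remove the mediated part of the prior-AF hazard ratio without any planned check detecting it. The direction for in-hospital AF follows from section 1.2. The size does not: the loss of about 12-39% of the log hazard ratio rests on the assumed frequencies and hazard ratios above, and it is smaller or larger if those change. For discharge drugs the prior-AF estimate would change meaning, but the direction is not known. This is an undefined target effect combined with a selection rule that cannot protect it. It is not a demonstrated wrong result, and it should be corrected before the models are fitted.

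**What to change.** In sections 7.1.1 and 7.4.1, state that the prior-AF hazard ratio is estimated with a pre-specified set of preoperative confounders, entered without univariate screening: demographics, comorbidities, cardiac status and imaging, planned procedure and urgency. Justify the set row by row against Table 1, because taking all preoperative and operative rows would bring the problem back. Leave out:

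- rows that restate or result from prior AF: History of arrhythmia, and preoperative antiarrhythmic and anticoagulant drugs where they are given for AF;
- rows measured after surgery: Postoperative duration (which sits in the Surgery block), complications, in-hospital AF and discharge drugs.

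Report a second model, labelled as prognostic or direct-effect, that adds in-hospital AF, complications and discharge drugs. Apply the negative-control and E-value analyses to the first model. Use the same distinction for any prior-AF estimate taken from the Poisson models in section 7.1.2.

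The cost is SAP wording and one extra model per outcome. No new data are needed, since every field is already in the planned extract, and the implied number of AF events easily supports the larger covariate set.
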